Prior treatment: radiation therapy ≥ 21 days of registration; RAI therapy ≥ 90 days of registration; Chemotherapy or targeted therapy ≥ 21 days of registration; any number of prior lines of therapy; No prior use of sorafenib or an mTOR inhibitor (see [§ 3.3.5](#))

No history of major surgery ≤ 28 days of registration

No history of intracranial brain metastasis

No history of ≤ 6 months of registration: myocardial infarction or unstable angina; New York Heart Association grade III or greater congestive heart failure; cerebrovascular accident; grade 3 or 4 peripheral ischemia or thromboembolic event (see [§ 3.3.8](#))

No history of liver disease as in [§ 3.3.9](#)

No history of gastrointestinal fistula or gastrointestinal perforation < 90 days of registration

No known history of prolonged QT syndrome

No Grade 3 or 4 hypertension that cannot be controlled with medication prior to registration (see [§ 3.3.12](#))

Concomitant medications: No chronic concomitant treatment with strong inhibitors of CYP3A4; No chronic concomitant treatment with strong CYP3A4 inducers; Patients requiring anticoagulation must be on stable dose of medication prior to registration (see [§ 3.3.13](#))

[figure not shown]
Not pregnant and not nursing (see [§ 3.3.14](#))

Age ≥ 18 years

ECOG Performance Status ≤ 2

Eligible patients must have histopathologically confirmed Hürthle cell thyroid cancer by central review

Schema, 1 Cycle = 28 days**

*PD= Progression of Disease

** 28-day cycle for 12 cycles (1 year). Starting with cycle 13, the cycle length will be 56 days.

Treatment is to continue until disease progression or unacceptable adverse event.

Patients will be followed for five years or until death, whichever comes first.

Please refer to the full protocol text for a complete description of the eligibility criteria and treatment plan.

Table of Contents

Section		Page
1.0 INTRODUCTION		7
1.1 Sorafenib.....		8
1.2 Everolimus.....		8
1.3 Combination of sorafenib and temsirolimus/everolimus in cancers other than thyroid cancer...		9
1.4 Hürthle cell thyroid cancer		10
1.5 Clinical experience of sorafenib and everolimus in RAI-refractory thyroid cancer.....		10
2.0 OBJECTIVES		11
2.1 Primary objective.....		11
2.2 Secondary objective.....		11
3.0 PATIENT SELECTION		11
3.1 On-Study Guidelines		11
3.2 Pre-Registration Eligibility Criteria.....		12
3.3 Registration Eligibility Criteria		12
4.0 PATIENT REGISTRATION.....		14

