2.2 Secondary objective

To compare the confirmed response rate, overall survival (OS), and adverse event rates between sorafenib and everolimus vs. sorafenib alone.

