7.0 TREATMENT PLAN/INTERVENTION

Protocol treatment is to begin \leq 14 days of registration. For questions regarding treatment, please see the study contacts page.

This phase II randomized study is comparing sorafenib alone (standard treatment at 400 mg orally twice a day) to the combination of sorafenib (400 mg orally twice a day) and everolimus (5mg orally once a day) in patients with RAI-refractory Hürthle cell thyroid cancer. This would be a 1:1 randomization.

In patients who are randomized to sorafenib alone, we would allow for a crossover to everolimus alone (10 mg orally daily) at time of progression as an exploratory cohort. If a patient does crossover to everolimus alone, everolimus must begin within 6 weeks of the last dose of sorafenib on study. If restaging imaging has not been done within 28 days before treatment with everolimus alone, it must be repeated.

At the time of crossover, pregnancy test must be repeated. Also, if it has been more than 3 months since the last lipid profile, the lipid profile must be repeated at crossover. Other lab tests and observations will be performed per study calendar in [Section 5.0](#).

Patients will remain on treatment as long as there is no progression of disease, excessive toxicity requiring the patient to come off of treatment, or the patient withdraws from treatment.

Arm 1:

Agent	Dose and Route	Frequency	Cycle Length (ReRx)
Sorafenib*	400 mg PO	Twice daily	28 days***

Arm 2:

Agent	Dose and Route	Frequency	Cycle Length (ReRx)
Sorafenib*	400 mg PO	Twice daily	28 days***
Everolimus**	5 mg PO	Once daily	28 days***

Crossover for Arm 1:

Agent	Dose and Route	Frequency	Cycle Length (ReRx)
Everolimus**	10 mg PO	Once daily	28 days***

* Sorafenib should be taken twice daily on an empty stomach one hour before or two hours after eating. This tablet should be swallowed whole and cannot be crushed or chewed.

** Everolimus should be administered once daily at approximately the same time each day with or without food. Tablets should be swallowed whole with a glass of water. The tablets must not be chewed or crushed and grapefruit juice or grapefruit should be avoided.

***After year 1, at the start of cycle 13, the cycle length will be 56 days.

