9.2 CTCAE Routine Study Reporting Requirements

***Combinations of CTCAE Grade & Attribution Required for Routine AE Data Submission on Case Report Forms (CRFs)**

Attribution	Grade 1	Grade 2	Grade 3	Grade 4	Grade 5
Unrelated			a	a	a
Unlikely			a	a	a
Possible		a	a, b	a, b	a, b
Probable		a	a, b	a, b	a, b
Definite		a	a, b	a, b	a, b

- a) Adverse Events: Other CRF - Applies to AEs occurring between registration and within 30 days of the patient's last treatment date, or as part of the Clinical Follow-Up Phase.
- b) Adverse Events: Late CRF - Applies to AEs occurring greater than 30 days after the patient's last treatment date.

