12.0 END OF TREATMENT/INTERVENTION

12.1 Duration of Treatment

12.1.1 CR, PR, or SD: Patients who are in CR, PR or SD will continue on therapy until disease progression.

12.1.2 Disease Progression: Give a minimum of 6 weeks of therapy. Remove from protocol therapy any patient with disease progression. Document details, including tumor measurements, on data forms.

After disease progression, patients should be followed for survival per the study calendar ([Section 5.0](#)).

12.1.3 Discontinuation of study agent: If the patient discontinues [study agent(s)], patients should be followed for survival per the study calendar ([Section 5.0](#)).

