13.0 STATISTICAL CONSIDERATIONS

13.1 Study Overview

This randomized Phase II trial will compare the progression-free survival (PFS) of sorafenib and everolimus vs. sorafenib alone in patients with radioactive iodine refractory hürthle cell thyroid cancer. Prior studies have shown that the median PFS is generally around 4.5 months for sorafenib alone in this disease population²⁹. It is hoped that the combination of everolimus and sorafenib can increase the median PFS to at least 9 months. In addition to PFS, this trial will also compare the confirmed response rate, overall survival (OS), and adverse event rates between sorafenib and everolimus vs. sorafenib alone.

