13.3 Secondary Endpoints

The following endpoints will be compared between the 2 arms: confirmed response rate, overall survival, and adverse events.

Confirmed Response Rate: A patient will be classified as a confirmed response per the RECIST 1.1 criteria, if they have a partial or complete response for 2 consecutive evaluations at least 4 weeks apart. The proportion of patients with a confirmed response will be calculated and compared between the 2 arms using a Chi-square or Fisher's Exact test.

Overall Survival: Overall survival (OS) is defined as the time from study entry to death from any cause. OS will be estimated using the Kaplan-Meier method, where the log-rank test will be used to compare the 2 treatment arms.

Adverse events: The maximum grade for each type of adverse event will be summarized using CTCAE version 4.0. The frequency and percentage of grade 3+ adverse events will be compared between the 2 treatment arms. Comparisons between arms will be made by using either the Chi-square or Fisher's Exact test.

Crossover patients exploratory analysis: In the crossover group that receives everolimus alone, we will assess both the response rate and progression-free survival as an exploratory analysis.

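### Grade 3+ adverse events are compared only as crude percentages; if the combination prolongs treatment, longer observation alone can raise its percentage

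*Combined protocol and SAP*

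**What the plan says.** The secondary objective in section 2.2 is "To compare the confirmed response rate, overall survival (OS), and adverse event rates between sorafenib and everolimus vs. sorafenib alone". Section 13.3 carries out the adverse event part in two steps. It summarises the maximum grade of each event type, and then: "The frequency and percentage of grade 3+ adverse events will be compared between the 2 treatment arms". The method is given as "Comparisons between arms will be made by using either the Chi-square or" Fisher's exact test. No person-time denominator, fixed window or time-to-event method for adverse events appears in 13.3 or elsewhere in the documents.

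Treatment has no fixed length. Section 7.0 says: "Patients will remain on treatment as long as there is no progression of disease", and adds excessive toxicity and withdrawal as reasons to stop. Section 12.1 agrees: "Patients who are in CR, PR or SD will continue on therapy until disease progression".

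Routine capture is tied to treatment. In section 9.2, note (a) to the reporting table reads: "Applies to AEs occurring between registration and within 30 days of the patient's last treatment date". The note goes on to include the clinical follow-up phase. Note (b) provides a late form for grade 3 to 5 events that are at least possibly related and occur more than 30 days after last treatment.

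On the size of the hoped-for effect, section 13.1 says: "It is hoped that the combination of everolimus and sorafenib can increase the median PFS to at least 9 months". The control assumption is 4.5 months.

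Sections 4.5 and 7.0 let sorafenib-arm patients start everolimus at progression, within 6 weeks of the last sorafenib dose. Section 13.3 does not say whether adverse events on that treatment count in the sorafenib arm.

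**The concern.** A crude percentage answers how many patients had at least one grade 3+ event while they were watched. When patients are treated to progression, how long they are watched depends on efficacy. Under the plan's own alternative, the combination arm is at risk for about twice as long on assigned treatment, so identical hazards give different percentages. A reader of 13.3 could not tell toxicity added by everolimus from extra months on sorafenib.

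This matters most when the trial is positive, because the tolerability estimate would then weigh in any decision on further development. The undefined handling of crossover events adds a second difficulty. Depending on how they are counted, sorafenib-arm exposure may or may not include a second drug, so the comparison itself is not fully specified.

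**Working it through.** **The plan's own figures.** The stated hazard ratio is 4.5/9 = 0.50. With 28 events, one-sided alpha 0.20 and one futility look at 14 events (stop if HR > 1), the drift is ln 2 × √28 / 2 = 1.834. The probability of passing the look and exceeding 0.842 at the end is 80.3%, matching the stated 80% power. The plan gives no figure for the adverse event comparison.

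**Inputs.**
- Median time on treatment of 4.5 and 9 months, taking PFS from 13.1 and 13.2 as exposure. Exponential exit rates are l = ln 2/4.5 = 0.1540 and ln 2/9 = 0.0770 per month; means are 6.5 and 13.0 months.
- Grade 3+ hazard a: not in the documents. Assumed equal in both arms and set so that 50% of sorafenib patients have an event.
- T, the months during which risk exists: varied.

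**Crude percentage.** P = a/(a+l) × [1 − exp(−(a+l)T)].

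| Risk confined to | a per month | Sorafenib | Combination | Excess (points) |
|---|---|---|---|---|
| 3 months | 0.308 | 50% | 54.8% | 4.8 |
| 6 months | 0.202 | 50% | 58.8% | 8.8 |
| 12 months | 0.161 | 50% | 63.8% | 13.8 |
| no limit (constant) | 0.154 | 50% | 66.7% | 16.7 |

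For the last row, 0.154/(0.154 + 0.077) = 0.667. With a constant hazard and sorafenib percentages from 10% to 80%, the excess is 8 to 17 points. Adding the 30-day tail makes it 7 to 16. If risk lasts only 1 month, the excess is 1 to 2 points at sorafenib percentages of 30% to 50%.

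**Exits for toxicity.** Section 1.1 reports that 18.8% stopped sorafenib for adverse events in the phase III trial. Add an exit rate d = l × s/(1−s), where s is the share leaving for toxicity, so total exit is l/(1−s). For sorafenib this is 0.1540/0.812 = 0.1897. If s on the combination is 30%, 40% or 50%, the exposure ratio falls from 2.0 to 1.72, 1.48 or 1.23. At constant hazard, 50% on sorafenib then becomes 63.3%, 59.6% or 55.2%. The direction reverses only when s exceeds 1 − 0.0770/0.1897 = 59%.

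**Effect on the test.** At 15 per arm and constant equal hazard, the combination has the higher observed count in 65% to 78% of trials. Fisher's test at two-sided 0.05 (a level assumed here; 13.3 states none) rejects in 3% to 7%.

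**Would events per patient-month solve it?** Count follow-up to the first event or exit: M = [1 − exp(−(a+l)T)]/(a+l) + exp(−(a+l)T)/l. With risk in the first 3 months only, sorafenib gives 0.500/3.25 = 0.154 and the combination 0.548/5.87 = 0.093, a ratio of 0.61 under equal hazards. With 6 months the ratio is 0.71. It is 1.00 only when the hazard is constant.

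**Would a fixed-time incidence with progression as a competing exit solve it?** At constant hazard and 48 weeks (11.0 months) it gives 48% against 61%, so 13 of the 17 points remain. At 16 weeks (3.68 months) it gives 0.500 × (1 − e^(−0.308×3.68)) = 34% against 0.667 × (1 − e^(−0.231×3.68)) = 38%, about 4 points. An early window reduces the distortion without removing it.

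**Time to first event, censored at end of assigned treatment.** At each time the two arms are compared among patients still at risk, so equal hazards give a cause-specific hazard ratio of 1.00 whether risk is early or constant.

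**The case against.** The strongest reply is that the distortion is conditional, and its direction is not settled by the text. It needs a real prolongation of treatment and a risk that persists. Treatment also stops for toxicity, withdrawal or a 4-week hold, and about three quarters of patients needed dose modification or reduction in the earlier studies cited in sections 1.1 and 1.3. A constant hazard is therefore the least favourable case. Related grade 3+ events remain reportable beyond 30 days, and events after crossover may extend the sorafenib arm's window. All of this stands, and it limits the size and certainty of the point.

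The crude percentage is also a legitimate description of total burden under treat-to-progression therapy. It should stay.

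Four stronger readings are tempting:
- That the plan guarantees a bias against the combination. The documents do not support this, for the reasons just given.
- That the 500-day median time on study in section 1.5 implies 79% against 50%. That pairs an interim figure from nine patients in one study with a 4.5-month PFS from another.
- That the term rates in section 2.2 contradicts the percentages in 13.3. The same sentence speaks of a response rate, which 13.3 defines as a proportion.
- That added toxicity cannot be distinguished at all. The maximum grade is summarised by event type, which gives some information.

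The practical consequence is also modest: the comparison is secondary, with 15 to 17 patients per arm. The harm is a distorted estimate more than a false significant test.

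**Conclusion.** The point holds in conditional form. Section 13.3 offers only a crude comparison in a design where success lengthens observation in one arm. If median treatment time doubles as hypothesised and hazards are equal, an assumed 50% on sorafenib becomes about 55% on the combination when risk is confined to the first 3 months, and at most 67% when it is constant. These figures rest on exponential time on treatment, PFS standing in for exposure, and an assumed hazard. They shrink with more toxicity stops on the combination and vanish if PFS does not differ. How crossover events are counted could shrink or reverse them, so that rule needs to be stated in any case. This is an inexpensive improvement to a secondary analysis. The primary endpoint, sample size and adverse event stopping rule in 13.7 are not affected.

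**What to change.** In section 13.3, keep the maximum-grade summary and the crude percentage, described as total burden, and add:

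1. Time to first grade 3+ adverse event from start of treatment, censored at the earliest of last dose of assigned treatment plus 30 days, start of crossover everolimus, or data cut-off. Compare arms by log-rank test with a cause-specific hazard ratio and interval.
2. The percentage with a grade 3+ event within a fixed early window, for example the first 16 weeks, under the same crossover cut-off.
3. A statement that events after crossover are tabulated separately and not counted in the sorafenib arm.

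Read the between-arm toxicity comparison from these together with the crude table. Do not rely on a simple events-per-patient-month rate, which can make the combination look falsely safer when toxicity is early.

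The cost is a few lines of text and one extra table, with wide intervals at this sample size. The documents do not confirm that onset dates of adverse events are collected. Timing may be known only to the cycle, and more coarsely after cycle 12, when cycles last 56 days and events can be collected every other cycle. The early window is least affected by this.

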13.4 Total Sample Size

A maximum of 30 evaluable patients will be accrued onto this randomized phase II study unless the study is closed early for excessive toxicity or lack of efficacy. We anticipate accruing an additional 10% of patients to account for ineligibility, cancellation, major treatment violation, or other reasons. Therefore, maximum accrual is 34 patients (17 per arm).

13.5 Expected Accrual and Accrual Duration

The expected accrual rate is about 1 patient per month for the Alliance group. With this accrual rate, we expect to finish accrual within about 36 months, assuming we accrue 34 total patients.

13.6 Anticipated time to study completion

We anticipate that the study will take approximately 5 years to complete. This allows a 12-month follow-up for the final patient enrolled, along with data entry, data clean-up, and analysis.

13.7 AE Stopping Rule

The stopping rule specified below is based on the knowledge available at study development. We note that the Adverse Event Stopping Rule may be adjusted in the event of either (1) the study re-opening to accrual after any temporary suspension or (2) at any time during the conduct of the trial and in consideration of newly acquired information regarding the adverse event profile of the treatment(s) under investigation. The study team may also choose to suspend accrual because of unexpected adverse event profiles that have not crossed the specified rule below.

Accrual will be temporarily suspended to this study if at any time we observe events considered at least possibly related to study treatment (i.e., an adverse event with attribute specified as "possible", "probable", or "definite") that satisfy any of the following criteria for each arm separately:

- If at any time, 3 of the initial 10 treated patients or 30% or more of all patients (i.e. when accrual is greater than 10 patients) have experienced a grade 4 adverse event.
- If at any time, 2 patients have experienced a grade 5 adverse event (not due to progressive disease).

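### In section 13.7, one treatment-related death with no separately recorded grade 4 event counts toward neither mandatory suspension threshold

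*Combined protocol and SAP*

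**What the plan says.** Section 13.7 suspends accrual temporarily on "events considered at least possibly related to study treatment" that "satisfy any of the following criteria for each arm separately". There are two criteria, and either one is enough.

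- **30% criterion.** Either "3 of the initial 10 treated patients" or, beyond 10, "30% or more of all patients (i.e. when accrual is greater than 10 patients) have experienced a grade 4 adverse event".
- **Death criterion.** "If at any time, 2 patients have experienced a grade 5 adverse event (not due to progressive disease".

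No sentence adds grade 4 and grade 5 patients together. Section 13.3, on the adverse event comparison, puts a plus sign after grade 3 when it means that grade and above. Section 13.7 has no such sign after grade 4.

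The section also leaves room for judgement: "The study team may also choose to suspend accrual because of unexpected adverse event profiles that have not crossed the specified rule below". It allows the rule itself to be adjusted when new information on adverse events arrives. Section 13.4 caps accrual at 34 patients, 17 per arm.

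**The concern.** Section 13.7 holds the plan's only numerical toxicity boundary. The interim analysis in 13.2 tests futility on PFS, and 13.8 monitors accrual. A boundary set at 30% life-threatening toxicity would be expected to count a fatal related event at least as readily as a grade 4 one. As worded, the first related death in an arm adds nothing to the 30% count unless that patient also had a related grade 4 event on record, and by itself it does not meet the death criterion. When the threshold is 3 of 10 and an arm has at most 17 patients, one uncounted patient can decide whether accrual pauses for review.

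**Working it through.** **Inputs from the documents.** 3 of the first 10 treated; 30% or more beyond 10; 2 deaths at any time; each arm separately (13.7). Maximum 17 per arm (13.4).

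**The plan's own figures.** 3/10 = 30%, so the two parts of the 30% criterion agree. 30/0.9 = 33.3, which gives 34 patients, or 17 per arm.

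**Largest combined count that crosses neither criterion.** Beyond 10 patients the threshold is the smallest whole number that is at least 0.3n. One fewer grade 4 patient, plus one death with no separate grade 4 event, crosses nothing:

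| n in arm | Grade 4 patients needed | Grade 4 + deaths, no trigger | Combined rate |
|---|---|---|---|
| 10 | 3 | 2 + 1 = 3 | 30.0% |
| 11 | 4 | 3 + 1 = 4 | 36.4% |
| 12 | 4 | 3 + 1 = 4 | 33.3% |
| 13 | 4 | 3 + 1 = 4 | 30.8% |
| 14 | 5 | 4 + 1 = 5 | 35.7% |
| 15 | 5 | 4 + 1 = 5 | 33.3% |
| 16 | 5 | 4 + 1 = 5 | 31.3% |
| 17 | 6 | 5 + 1 = 6 | 35.3% |

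The rows above 10 also require that no earlier look crossed the rule, for example at most 2 grade 4 patients among the first 10. A second death meets the death criterion, so the shortfall is never more than one patient per arm.

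**Probability within the first 10.** Assume independent patients, all treated, each classed by worst related grade, with rates p4 (grade 4) and p5 (grade 5), and q = 1 − p4 − p5. Counts only grow, so the rule has been crossed by patient 10 exactly when the counts at 10 cross it:

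P(as written) = 1 − Σ over d = 0, 1 and g = 0, 1, 2 of [10!/(g! d! (10−g−d)!)] p4^g p5^d q^(10−g−d)

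The two wordings differ only when there are exactly 2 grade 4 patients and 1 death:

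Difference = 10 × p5 × C(9,2) × p4² × q⁷ = 360 p5 p4² q⁷

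For p4 = 20%, p5 = 5%, q = 0.75:
- d = 0 terms: 0.0563 + 0.1502 + 0.1802 = 0.3867.
- d = 1 terms: 0.5 × (0.0751 + 0.1802 + 0.1922) = 0.2238.
- As written: 1 − 0.6104 = 39.0%.
- Difference: 360 × 0.05 × 0.04 × 0.1335 = 9.6 points, giving 48.6% if grade 4 and 5 both count.

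| Assumed grade 4 / grade 5 rate | As written | Grade 4 or 5 counted | Difference (points) |
|---|---|---|---|
| 10% / 1% | 7.4% | 9.0% | 1.6 |
| 10% / 3% | 10.3% | 14.4% | 4.1 |
| 20% / 1% | 32.6% | 35.3% | 2.8 |
| 20% / 5% | 39.0% | 48.6% | 9.6 |
| 20% / 10% | 52.5% | 64.3% | 11.9 |

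**By 17 patients.** Carrying the counts forward patient by patient, with the thresholds in the first table, gives 51.6% against 59.4% at 20%/5%, and 72.1% against 78.7% at 20%/10%.

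**If half of the fatal cases also had a recorded grade 4 event.** The difference then arises only when the single death is one without such a record, so it halves. At 20%/5% it is 9.6/2 = 4.8 points (43.8% against 48.6%).

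**The case against.** Separate criteria for grade 4 events and deaths are a legitimate design, and the death criterion is the stricter one: 2 deaths suspend at any size, and 2/17 is 11.8%. The action is only a temporary pause. The team may suspend below the rule, and section 9.3.1 requires a 24-hour report of a serious grade 5 event within 30 days of treatment, so a death would be known quickly. This stands, and it limits how much the gap matters. It does not close the gap, because the discretion is optional and is worded for unexpected adverse event profiles.

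The documents do not support three stronger readings that a reader might infer.

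- **A grade 4 event that becomes fatal leaves the count.** Section 13.7 counts patients who have experienced a grade 4 event, and nothing removes a patient later. The maximum-grade convention in 13.3 is for the adverse event summary. The calculation by worst grade therefore gives the upper end of the effect.
- **The rule is less sensitive when toxicity is worse.** With grade 4 held at 20%, raising grade 5 from 1% to 5% to 10% raises suspension in the first 10 from 32.6% to 39.0% to 52.5%. If the total is held at 30% and split 30/0, 25/5 or 20/10, the chance is 61.7%, 53.1% and 52.5% in the first 10, and 70.2%, 65.7% and 72.1% by 17 patients. There is a dip when deaths replace grade 4 events, which is the one-patient gap again, but no general loss of sensitivity.
- **The move from treated patients to all patients in the denominator is a second defect.** Four events in 13 is 30.8% and in 14 is 28.6%. But the rule applies at any time, so 4 of 13 suspends when it occurs and a later registration cannot undo it. An undosed 14th patient matters only if the fourth event falls between that registration and the first dose, a window of at most 14 days (7.0), while an arm gains about one patient every two months (13.5). A never-treated patient would stay in a literal count, but all patients can reasonably be read as all treated patients, and the effect was not modelled.

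The size also rests on chosen rates. At a 1% grade 5 rate the difference is only 1.6 to 2.8 points.

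**Conclusion.** The point holds in a narrow form. Followed exactly, 13.7 lets 30% to 36% of an arm have related grade 4 or 5 toxicity without mandatory suspension, when one of those patients died with no separate grade 4 event on record. The shortfall is at most one patient per arm. In the first 10 patients it lowers the chance of suspension by about 2 to 12 points for assumed grade 5 rates of 1% to 10% and grade 4 rates of 10% to 20%, and by about half as much if half of the fatal cases also had a recorded grade 4 event. All of these rates are assumptions. The documents state neither expected nor acceptable rates of related grade 4 and 5 events, so the figures show how sensitive the rule is to its wording and are not a forecast. If the authors meant grade 4 or higher, the text does not say so.

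**What to change.** In the 30% criterion of 13.7, replace the grade 4 condition with *a grade 4 or 5 adverse event (not due to progressive disease)*, counting each patient once. Leave the two-death criterion unchanged, so that a death counts toward both. Optionally, say treated patients in both parts of the 30% criterion; this is a clarification only.

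The change takes one sentence and an edit to the monitoring program. Its downside is the same quantity as its benefit: a higher chance of a temporary suspension, by 1.6 to 11.9 points in the first 10 patients over the rates shown (4.1 points at 10% grade 4 and 3% grade 5). Since no acceptable toxicity rate is stated, the study team has to judge whether that is worth it. For a pause to review a related death alongside grade 4 events, it seems a modest price.
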